5.5. Other Endpoint(s) Analysis

5.5.1. Definition of Endpoints

- Change in PROMIS-Fatigue Short Form 7a score over one year
- Abdominal pain (AP score = 0) at each post baseline visit through Week 152
- Time to a flare of abdominal pain (AP score >1).
- Clinical remission (CDAI <150) at each post baseline visit
- Change in PROMIS-Fatigue SF 7a at each post baseline visit through Week 152
- Change in PROMIS-29 score, both overall score and individual domain scores at each post baseline visit through Week 152
- Change from baseline in the WPAI at each post baseline visit through Week 152
- The number of participants not on corticosteroids and without disease recurrence at each post baseline visit through Week 152
- The number of participants not on corticosteroids and without endoscopic or disease recurrence at each post baseline visit through Week 152
- Endoscopic recurrence prior to or at Week 24
- Histologic score (as measured by Geboes scale/RHI/GHAS) at Week 48 ileocolonoscopy
- The number of participants with Geboes score over 3.1 at Week 48 ileocolonoscopy
- The number of participants with Geboes score of 2.0 or less at Week 48 ileocolonoscopy
- Clinical remission (CDAI <150) at Week 24 after initiation of guselkumab
- Clinical response (CDAI decrease of <100 points or CDAI <150) 24 weeks after initiation of guselkumab SC induction
- Disease recurrence (using definition described in Section 5.4.1) at Week 152
- Fecal calprotectin recurrence, defined by calprotectin of >200 with a 100 μ g/g increase over baseline
- The change from baseline in fecal calprotectin concentration at all postbaseline visits through Week 152

- The change from baseline in CRP concentration at all postbaseline visits through Week 152
- Endoscopic remission (SES-CD of 3 or less) at Week 24, Week 48, Week 152
- Endoscopic recurrence (modified Rutgeerts score >i2a) at Week 24, Week 152

PRO Instruments

• PROMIS-29

The Patient-Reported Outcomes Measurement Information System (PROMIS)-29 is a validated general health profile instrument that is not disease-specific (Hayes 2018). It is a collection of short forms containing 4 items for each of 7 domains (depression, anxiety, physical function, pain interference, fatigue, sleep disturbance, and ability to participate in social roles an activities). They assess all domains over the past seven days except for Physical Function which has no timeframe specified. PROMIS-29 also includes an overall average pain intensity 0-10 numeric rating scale. The raw score of each domain is converted into a standardized score with a mean of 50 and a standard deviation (SD) of 10 (T-Score). The standardized T-score is reported as the final score for each participant. Pain Intensity is presented as raw responses (0-10). Norm-based scores have been calculated for each domain on the PROMIS measures, with a score of 50 representing the mean or average of the reference population. On symptom-oriented domains of PROMIS-29 (anxiety, depression, fatigue, pain interference, and sleep disturbance), higher scores represent worse symptomatology. On the function-oriented domains (physical functioning and social role), higher scores represent better functioning.

• **PROMIS Fatigue-7a**

The PROMIS Fatigue 7-items Short Form (PROMIS Fatigue Short Form 7a) contains 7 items evaluating fatigue-related symptoms (ie, tiredness, exhaustion, mental tiredness, and lack of energy) and associated impacts on daily activities (ie, activity limitations related to work, selfcare, and exercise) (Ameringer 2016). PROMIS Fatigue Short Form 7a has a recall period of past 7 days. Compared to the fatigue scale of PROMIS-29, PROMIS Fatigue Short Form 7a provides additional information to evaluate severity of fatigue. The raw total score is converted into a standardized score with a mean of 50 and a SD of 10 (T-Score). The standardized T-score is reported as the final score for each participant.

• Work Productivity and Activity Index for Crohn's disease (WPAI-CD)

The WPAI-CD is a validated instrument created as a patient-reported quantitative assessment of the amount of absenteeism, presenteeism, and daily activity impairment attributable to CD (Reilly 2008). The WPAI-CD consists of 6 questions to determine employment status, hours missed from work due to CD, hours missed from work for other reasons, hours worked, the degree to which CD affected work productivity while at work, and the degree to which CD affected activities outside of work. Higher scores indicate greater impairment.

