5.1. Inclusion Criteria

Each potential participant must satisfy all of the following criteria to be enrolled in the study:

Age

1. Participants \geq 18 (or the legal age of consent in the jurisdiction in which the study is taking place).

Type of Participant and Disease Characteristic

- 2. Have a documented diagnosis of CD confirmed by endoscopic, histologic, and/or radiologic studies prior to resection or by tissue obtained at resection.
- 3. Have undergone an ileocolonic surgical resection (ie, an intestinal resection with an ileocolonic anastomosis) for CD prior to the baseline visit with the following criteria:
 - Have no known active CD anywhere in the gastrointestinal (GI) tract, including the findings at surgery,
 - Be able to undergo randomization no later than 49 days after surgery, and at least 10 days after surgery (or 8 days after resumption of bowel activity, eg, in case of postoperative ileus),
 - Ileocolonic resection was not for the purpose of removing known dysplasia,
 - If ileocolonic resection occurs > 10 years since the diagnosis of CD and only fibrostenotic stricturing is present, then length of stricture must be > 10 cm

4. Have a baseline CDAI < 200.

Concomitant or previous medical therapies received

- 5. Meets the following requirements for prior or current medications for CD. The following medications are permitted provided that doses meeting the requirements listed below are stable or have been discontinued within the timeframes prior to baseline specified below:
 - Oral corticosteroids at a prednisone-equivalent dose at or below 20 mg/day, or 9 mg/day of budesonide. Participants on corticosteroids should initiate/continue tapering after baseline, per the recommended schedule (see Section 6.8.1.1).
 - Conventional immunomodulators (ie, azathioprine [AZA], 6-mercaptopurine [6-MP], or methotrexate [MTX]) must be discontinued prior to randomization.

Screening Laboratory Tests

- 6. Have screening laboratory test results within the following parameters, and if 1 or more of the laboratory parameters are out of range, a single retest of laboratory values is permitted during the screening period:
 - a. Hemoglobin ≥8.0 g/dL (International System of Units [SI]: ≥80.0 g/L)
 - b. White blood cells $\ge 3.0 \times 10^3 / \mu L$ (SI: $\ge 3.0 \times 10^9 / L$)
 - c. Neutrophils $\geq 1.5 \times 10^3 / \mu L$ (SI: $\geq 1.5 \times 10^9 / L$)
 - d. Platelets $\geq 100 \times 10^3 / \mu L$ (SI: $\geq 100 \times 10^9 / L$)

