8.1.1. CDAI

The CDAI (Crohn's Disease Activity Index) will be assessed by collecting information on 8 different Crohn's disease-related variables (Best, 1976): extraintestinal manifestations, abdominal mass, weight hematocrit, total number of liquid or very soft stools, AP/cramping, use of antidiarrheal drug(s) and/or opiates, and general well-being (Appendix 9). The abdominal mass is assessed through physical examination. Total number of liquid or very soft stools, AP/cramping, use of antidiarrheal drug(s) and/or opiates, and general well-being are recorded by the participant on an electronic home diary or diary card on a daily basis.

8.1.2. PRO-2: Unweighted Mean Daily CDAI Components of the Total Number of Liquid or Very Soft Stools and the AP

The PRO-2 includes the CDAI components of the total number of liquid or very soft stools and the AP score.

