9.4.4. Other/Exploratory Endpoints

The other/exploratory endpoints include but are not limited to the endpoints described in Section 3. A complete list of the other endpoints will be provided in the SAP. The testing of these endpoints will not be controlled for multiplicity and nominal p-values will be provided.

Other endpoints include:

- Change in PROMIS-Fatigue Short Form 7a score over 48 weeks
- Abdominal pain (AP score = 0) at each post baseline visit through Week 152
- Time to a flare of abdominal pain
- Clinical remission (CDAI <150) at each post baseline visit
- Change in PROMIS-Fatigue SF 7a at each post baseline visit through Week 152
- Change in PROMIS-29 score, both overall score and individual domain scores at each post baseline visit through Week 152
- Change from baseline in the WPAI at each post baseline visit through Week 152
- The number of participants not on corticosteroids and without disease recurrence at each post baseline visit through Week 152
- The number of participants not on corticosteroids and without endoscopic or disease recurrence at each post baseline visit through Week 152
- Endoscopic recurrence prior to or at Week 24
- Histologic score (as measured by Geboes scale/RHI/GHAS) at Week 48 ileocolonoscopy
- The number of participants with Geboes score over 3.1 at Week 48 ileocolonoscopy

- The number of participants with Geboes score of 2.0 or less at Week 48 ileocolonoscopy
- Clinical remission (CDAI <150) at Week 24 after initiation of guselkumab SC induction
- Clinical response (CDAI decrease of <100 points or CDAI <150) 24 weeks after initiation of guselkumab SC induction
- Disease recurrence (using definition described in Section 9.4.3) at Week 152
- Fecal calprotectin recurrence, defined by calprotectin of >200 μg/g with a 100 μg/g increase over baseline
- The change from baseline in fecal calprotectin concentration at all postbaseline visits through Week 152
- The change from baseline in CRP concentration at all postbaseline visits through Week 152

An additional exploratory analysis for risk factors of endoscopic and disease recurrence will be performed. A sensitivity analysis of the primary endpoint will be performed using a Rutgeerts score of > i3 as the definition for endoscopic recurrence.

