5.4.1.1. Definition of Endpoint(s)

Clinical remission without disease recurrence is a composite endpoint defined by the following:

- CDAI < 150 at Week 48 and
- No endoscopic recurrence as defined by Rutgeerts score < i2a by Week 48 and
- Have not experienced a disease recurrence as defined below

Disease recurrence is a composite endpoint defined by the following:

- A ≥ 70-point increase from baseline in CDAI score at beyond 8 weeks after randomization; and a CDAI score of ≥ 200 **and** evidence of endoscopic recurrence. Endoscopic recurrence is defined as a modified Rutgeerts score of ≥ i2a at the anastomotic site or its equivalent elsewhere in the GI tract, unless a stool test for C. difficile toxin or other enteric pathogen is positive
- In event of a positive test for enteric pathogen including C. difficile toxin, the underlying infection should be treated and if ileocolonoscopy has not yet been performed, it should only be done when the infection has resolved, and if disease recurrence threshold is still met
- OR initiation of a physician-prescribed corticosteroids, or an increase in the dose of steroids already being taken (by greater than 5 mg/day), for over one week for the treatment of CD and evidence of endoscopic recurrence as described above, unless a stool test for C. difficile toxin or other enteric pathogen is positive
- OR a new draining external fistula
- OR the reopening and draining of a previously existing external fistula
- OR developing a new internal fistula
- OR developing a new perianal abscess
- OR developing a new intra-abdominal abscess more than three months after the date of the index surgery

Participants who have confirmed endoscopic recurrence without disease recurrence at Week 24 or Week 48 and cross over to open-label guselkumab treatment will be censored at cross over for the time to disease recurrence endpoint.

Abdominal pain free at Week 48 is defined as abdominal pain (AP) score = 0 at Week 48

Time-to-recurrence of symptoms is defined as time to attaining an AP mean daily score >1 (and also >1 point higher than baseline) along with stool frequency (SF) mean daily score >3 (and also >3 higher per day than baseline) for 2 consecutive weeks through Week 48. Participants who cross over to open-label guselkumab treatment and do not have recurrence of symptoms will be censored at cross over for the time to recurrence of symptoms endpoint.

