6.12.3. CDAI Score Calculation

Has the participant had a video ileocolonoscopy since the last site visit? Yes/no If yes,

[figure not shown]
Date of video ileocolonoscopy: _____

Date of the start of the bowel preparation: —

DISEASE ACTIVITY INDEX	SUM XFACTOR SUBTOTAL	
Total number of liquid or very soft stools in the previous 7 days	 	
Sum abdominal pain/cramps ratings		
(total for previous 7 days):	x 5 =	
0 = none $2 =$ moderate		
1 = mild $3 = severe$		
	_	
Sum general well-being ratings (total for previous 7 days):	x 7 =	
0 = generally well $3 = $ very poor		
1 = slightly under par $4 = $ terrible		
2 = poor		
Categories currently present and		
presumed to be related to Crohn's disease : $0 = no; 1 = yes$	•	
$\Box =$ arthritis/arthralgia	x 20 =	
$\Box = iritis/uveitis$	x 20 =	
$\Box =$ erythema nodosum/pyoderma gangrenosum/aphthous		
stomatitis	x 20 =	
$\Box =$ anal fissure, fistula or abscess	x 20 =	
$\Box =$ other fistula	x 20 =	
$\Box = $ fever over 100° F (37.8° C) during the previous 7		
days.	x 20 =	
During the previous 7 days has subject received antidiarrheal or		
opiate medications for diarrhea at least once:		
	x 30 =	
0 = no		
1 = yes		
Abdominal mass:	x 10 =	
0 = none $2 = $ questionable $5 = $ definite		
Hematocrit:	x 6 =	
Males: $(47-Hct) = SUM$	(add or subtract by sign)	
Females: $(42-Hct) = SUM$		
	*	
(Standard Weight - Actual Body Weight) x 100 =	x 1 =	
Standard Weight	(add or subtract by sign, round to 3 decimal places	s)
·o	, , , , , , , , , , , , , , , , , , ,	'
* If this value is less than -10 then enter -10 here.		
Standard weight and actual weight must be in same units (kg or	r lb)	
	TOTAL =	

(round total to integer)

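### The abdominal pain flare endpoint is AP score >1 with no baseline reference and no stated unit, so pain above 1 that persists from entry counts as a new flare.

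*SAP*

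**What the plan says.** The whole definition in SAP 5.5.1 is "Time to a flare of abdominal pain (AP score >1"). Protocol 9.4.4 lists the endpoint only as "Time to a flare of abdominal pain", with no threshold. Abdominal pain is a CDAI diary item scored 0 (none), 1 (mild), 2 (moderate) or 3 (severe) (SAP Appendix 12). According to Protocol 8.1.1, the diary items "are recorded by the participant on an electronic home diary or diary card on a daily basis".

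For exploratory time-to-event endpoints, SAP 5.5.2 adds intercurrent-event rules, medians, Kaplan-Meier curves and a log-rank test stratified by baseline CDAI remission, region and number of prior surgeries. It has no stratum, exclusion or adjustment for baseline AP.

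SAP 5.4.1.1 handles pain differently in time to recurrence of symptoms. There the AP part is "an AP mean daily score >1 (and also >1 point higher than baseline"), and a parallel stool-frequency criterion must also be met, for two consecutive weeks.

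On entry, Protocol 5.1 requires a baseline CDAI below 200 and sets no AP limit. Randomization may take place "at least 10 days after surgery (or 8 days after resumption of bowel activity") and no later than 49 days after surgery.

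**The concern.** A flare is a worsening. A bare threshold cannot tell new pain from pain that was there at randomization. In a population recruited from 10 days after a bowel resection, some participants may enter with moderate pain. Under the rule as written, each of them whose score is still above 1 at the first post-baseline assessment is an event, however much the pain is improving. Study treatment can have little bearing on events of this kind, and randomization should spread them evenly over the arms. They add noise to the comparison without adding information.

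The plan's comparable worsening endpoints each pair a threshold with a rise from baseline:
- symptom recurrence, as described above;
- the CDAI criterion of disease recurrence (at least 200, with a rise of at least 70);
- fecal calprotectin recurrence (above 200, with a rise of 100 µg/g), which stands in the same SAP 5.5.1 list.

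The pain flare lacks this element, and no reason is given.

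**Working it through.** The documents give no event rate, sample size or power for this endpoint, so there is no stated figure to reproduce.

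**Step 1: can a participant enter with AP above 1?** The CDAI weights the sum of seven daily AP ratings by 5 (SAP Appendix 12).

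| Daily AP | CDAI points | Left under entry limit (max 199) | Left under remission cut-off (max 149) |
|---|---|---|---|
| 1 | 1 × 7 × 5 = 35 | 164 | 114 |
| 2 | 2 × 7 × 5 = 70 | 129 | 79 |
| 3 | 3 × 7 × 5 = 105 | 94 | 44 |

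So yes: even a participant in CDAI remission at baseline can already satisfy AP >1. The baseline table in SAP Appendix 3 has categories for AP of 2 or more, so it provides for such participants. A rating of 1 does not meet the threshold.

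**Step 2: when would the event be counted?** That depends on the missing unit. With a single daily rating it is the first diary day above 1. With a 7-day mean it is the first window. With a visit value the first scheduled visit is Week 8, nominally 10 + 56 = 66 days after surgery for the earliest-randomized participant. In each case pre-existing pain that is still above 1 counts; only the number of such participants changes.

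**Step 3: how much dilution?** Assumptions, none of them from the documents for this endpoint: 185 per arm; later flares of 20% on placebo and 10% on guselkumab; a share q of each arm with an event at the start. The event proportions become a = q + (1 − q) × 0.20 and b = q + (1 − q) × 0.10. For the formula, HR = ln(1 − b) / ln(1 − a), events D = 185 × (a + b), and power = Φ(|ln HR| × √D / 2 − 1.96). Because a spike at entry breaks proportional hazards, the log-rank test was also simulated directly (unstratified, 8,000 runs per row, early events counted as events).

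| q | a v b | D | Implied HR | Formula power | Simulated power |
|---|---|---|---|---|---|
| 0 | 20.0% v 10.0% | 55.5 | 0.47 | 80% | 78% |
| 5% | 24.0% v 14.5% | 71.2 | 0.57 | 66% | 61% |
| 10% | 28.0% v 19.0% | 87.0 | 0.64 | 54% | 51% |
| 15% | 32.0% v 23.5% | 102.7 | 0.69 | 45% | 42% |

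As rounded figures between the two methods, power falls from about 80% to about 65%, 53% or 43%. The HR column is only a step in the formula, since SAP 5.5.2 plans no hazard ratio for this endpoint.

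**Step 4: what if those participants are left out?** The same simulation without them gives about 76%, 74% and 71% at q = 5%, 10% and 15%. Most of the loss therefore comes from counting them as events, and little from the smaller sample.

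**The case against.** A reader might infer that everyone who enters with postoperative pain is a flare on the first diary day, and that for anyone else one bad day is enough. The documents do not support that. A rating of 1 is not an event. Pain above 1 at baseline may have fallen by the first assessment. The unit of the score is also unstated: the neighbouring item in SAP 5.5.1 uses AP score per visit, and Protocol 8.1.2 describes the PRO-2 components as daily means. On a visit reading, only pain lasting to about Week 8 would count, and the early-event share could be far smaller than the illustration. This stands, and it limits the point to scores above 1 that persist to the first assessment, whenever that is.

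A reader might also infer a biased hazard ratio. SAP 5.5.2 plans a stratified log-rank test here and no Cox model, and the early events are expected equally in both randomized arms. The consequence is dilution, with no direction in favour of either arm.

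Absolute thresholds are not foreign to the plan: abdominal pain free (AP = 0) has no baseline reference. But that endpoint asks for a state at a given time, where present status is the question. Time to a flare asks for a new event. Symptom recurrence is also a joint pain and stool-frequency endpoint, so it is a precedent for the AP wording only and not a template to be copied whole.

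Lastly, the endpoint is exploratory with nominal p-values. SAP Section 1 says that only four participants were enrolled and that the planned analyses are kept for reference. This bears on priority and leaves the defect in the definition as it is.

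**Conclusion.** The point holds in a limited form. As written, the definition counts pain above 1 that was present at entry, and is still above 1 at the first post-baseline assessment, as a flare without any worsening. The entry criteria allow such participants, and nothing in SAP 5.5.2 removes them. The endpoint therefore does not measure new flare, and the comparison is diluted in both arms.

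The size cannot be fixed from the documents, because they do not report how many participants enter above 1. The power figures rest wholly on the assumed 20% v 10% rates and the 5% to 15% share, and they shrink if AP is read at visits from Week 8. The 20% v 10% pair equals the plan's assumption for disease recurrence and is used here only as a convenient example. Impact on the trial's conclusions is low.

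**What to change.** In SAP 5.5.1, define the flare as a 7-day mean AP score above 1 and more than 1 point above the baseline 7-day mean, which is the AP part of the wording in 5.4.1.1. The baseline mean is obtainable, since Protocol Section 8 already requires at least 7 days of CDAI diary data in screening.

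The rise alone is not enough. On a 0-3 scale a participant with a baseline mean of 2 or more would need a score above 3 and could never flare, so automatic events would be replaced by impossible ones. Add one of two rules:
- Restrict the endpoint to participants with a baseline mean AP of 1 or below. This is the simpler choice, because it selects on a pre-randomization value.
- For participants above 1, start time at risk when the mean has fallen to 1 or below, and measure the rise from that later value. Without the reset the ceiling remains. This rule conditions on a post-randomization event, which should be acknowledged.

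The cost is a sentence or two in the SAP and a somewhat smaller at-risk set for one exploratory endpoint. In the illustration, restriction leaves power at about 71% to 76%, against 42% to 61% in the same simulation under the present wording.

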6.5.1. Open Label / Cross over Treatment

Starting after the Week 8 visit, if disease recurrence is confirmed and the definition as described in Section 9.4.3 is satisfied, participants will cross over to open-label treatment with guselkumab. Similarly, participants who are determined to have endoscopic recurrence by central read on the Week 48 or flare visit ileocolonoscopy will also cross over to open-label treatment; for the optional Week 24 ileocolonoscopy, if the central reader confirms endoscopic recurrence (modified Rutgeerts score of i2a or greater), cross over may be done at the discretion of the principal investigator with the participant's agreement. If a participant does not cross over at Week 24 for endoscopic recurrence but, within the following 16 weeks, develops an increase in CDAI \geq 70 or meets the corticosteroid-related disease recurrence criteria (see Section 9.4.3), then the participant may cross over without the need for a repeat ileocolonoscopy.

As discussed in Section 8, at the cross over visit, participants, regardless of the treatment arm to which they were randomized, will receive guselkumab for 3 doses, followed by maintenance guselkumab This regimen matches the regimen under study in the ongoing Phase 3 study, CRD3004. The induction will be open-label and the participant and investigator will remain blinded to original randomized treatment assignment. Participants will not be allowed to cross over after the Week 128 visit and, while awaiting their confirmatory ileocolonoscopy, regularly scheduled study intervention may be held.

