5.3. Primary Endpoint(s) Analysis

5.3.1. Definition of Endpoint

The primary endpoint is endoscopic recurrence prior to or at Week 48 as defined by modified Rutgeerts score \geq i2a in the neo-terminal ileum, anastomotic site, or its equivalent elsewhere in the GI tract (eg, colonic ulceration).

Rutgeerts score

Score	Endoscopic Findings
i0	No lesions
i1	< 5 aphthous lesions
i2	> 5 aphthous lesions with normal mucosa between the lesions or skip areas of larger lesions or lesions confined to the ileocolonic anastomosis (ie, < 1 cm in length)
i2a	Lesions confined to the ileocolonic anastomosis (including anastomotic stenosis)
i2b	More than 5 aphthous ulcers or larger lesions, with normal mucosa in-between, in the neoterminal ileum (with or without anastomotic lesions)
i3	Diffuse aphthous ileitis with diffusely inflamed mucosa
i4	Large ulcers with diffuse mucosal inflammation or nodules or stenosis in the neoterminal ileum

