5.3.2. Estimand

5.3.2.1. Primary Estimand

An estimand is a precise definition of the primary targeted treatment effect defined by the following 5 attributes: Study Intervention, population, variable (endpoint), intercurrent events (ICEs) and corresponding strategies, and population-level summary.

Primary Trial Objective: To evaluate the efficacy of guselkumab treatment prior to or at Week 48 compared with placebo in preventing endoscopic recurrence of CD in participants after surgery.

Estimand Scientific Question of Interest: What is the proportion of participants developing endoscopic recurrence prior to or at Week 48, and thus considered to have benefited from guselkumab versus placebo?

Study intervention:

- Experimental: Guselkumab ^{CCI} at Week 0 and then ^{CCI} at Week 8, then ^{CCI} thereafter through the end of the total study period.
- Control: Matched placebo CCI at Weeks 0 and 8 and then CCI thereafter through the end of the total study period.

Population: Participants with recent (<49 days) qualifying surgery and no evidence of active Crohn's disease postoperatively.

Variable: A binary recurrence variable (recurrence/no recurrence) where recurrence is defined as Endoscopic Recurrence prior to or at Week 48 (as defined by modified Rutgeerts score greater than or equal to i2a in the neo-terminal ileum, anastomotic site, or its equivalent elsewhere in the GI tract (eg, colonic ulceration)) or experiencing intercurrent events (ICEs) 1-4 presented below.

Summary Measure (Population-level summary): Difference in proportions of the binary recurrence variable of endoscopic recurrence, as described above, between guselkumab group and the placebo group.

Intercurrent events and their corresponding strategies:

The ICEs considered for this study are listed in Table 7:

Table 7:	Intercurrent Events and Corresponding Analysis Strategies for Endoscopic Recurrence prior to
	or at Week 48

Inte	ercurrent Events (between baseline and Week 48)	Analysis Strategy for Intercurrent Events
1. 2.	A CD-related surgery (with the exception of minor procedures such as drainage of a superficial abscess or seton placement, etc.) A prohibited change in CD medication	
3. 4.	Discontinuation of study intervention due to lack of efficacy or an AE of worsening CD Cross over to open-label guselkumab	

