5.5.2. Analysis Methods

Unless otherwise specified, the exploratory endpoints listed and defined in Section 5.5.1 will be analyzed based on the FAS according to the randomized intervention group regardless of the intervention actually received.

All exploratory endpoints will be tested regardless of the significance of the primary and secondary endpoints; the testing of these endpoints will not be controlled for multiplicity. Nominal p-values will be presented.

Descriptive statistics (ie, N, mean, median, SD, IQ range, minimum, and maximum) will be used to summarize continuous variables. Frequency counts and percentages will be used to summarize categorical variables. Graphical data displays (eg, line plots) may also be used to summarize the data.

Binary Endpoints

The intercurrent events captured for binary endpoints specified in Section 5.3.2 will be applied to each of the above binary endpoints. Participants with ICEs in categories 1-4 will be considered to have unfavored outcome. For participants experiencing an ICE 5 and ICE 6, their observed values will be used, if available.

Participants with any missing data for an endpoint after accounting for the ICEs will be imputed as having unfavored outcome. Binary endpoints will be summarized with the number and frequency of participants who achieve the endpoint by treatment group. Treatment comparisons will be performed using CMH chi-square test stratified by clinical remission status at baseline (CDAI < 150, CDAI \ge 150), region (North America, Western Europe, rest of world) and number of prior surgeries (1 surgery versus > 1 surgery, with the qualifying surgery counting as 1 surgery). In case of rare events, the Fisher's exact test will be used for treatment comparisons.

Time-to-event Endpoints

The ICEs captured for time-to-event endpoints specified in Section 5.4.1 will be applied to each of the above time-to-event endpoints. Participants with ICEs in categories 1-3 will be considered to have unfavored outcome. For participants experiencing an ICE 4 and ICE 5, their observed values will be used, if available.

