5.6.2.1. Definition of Endpoints

- Clinical remission (CDAI < 150) at 24 weeks after initiation of guselkumab SC induction
- Clinical response (CDAI decrease of <100 points or CDAI <150) at 24 weeks after initiation of guselkumab SC induction
- Endoscopic remission (SES-CD of 3 or less) at 24 weeks after guselkumab SC induction
- Endoscopic remission (modified Rutgeerts score <i2a) at 24 weeks after guselkumab SC induction

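### The exploratory Week 24 and Week 152 endoscopic recurrence endpoint uses > i2a, while the primary endpoint and the Week 24 cross over rule count i2a, and no reason is given

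*SAP*

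**What the plan says.** Three uses of the modified Rutgeerts score matter here.

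- **Primary endpoint.** SAP 5.3.2.1 gives the threshold in words: "as defined by modified Rutgeerts score greater than or equal to i2a in the neo-terminal ileum". It applies to any reading up to and including Week 48.
- **Week 24 cross over.** Protocol 6.5.1 makes cross over after the optional Week 24 ileocolonoscopy possible "if the central reader confirms endoscopic recurrence (modified Rutgeerts score of i2a or greater").
- **Exploratory recurrence.** SAP 5.5.1 lists "Endoscopic recurrence (modified Rutgeerts score >i2a) at Week 24, Week 152". The same strict sign appears in SAP 1.1 and in Protocol 1.1 and 3.

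The SAP 5.5.1 list also contains "Endoscopic recurrence prior to or at Week 24", with no threshold; Protocol 9.4.4 has the same entry. In SAP 5.3.1 the category at issue, i2a, is "Lesions confined to the ileocolonic anastomosis (including anastomotic stenosis").

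**The concern.** One word, recurrence, has two cut-offs, and neither document explains the difference. Protocol 8.1.3 points towards counting i2a: it describes ≥ i2a as the standard outcome in most trials in this setting, and it cites studies that found no difference in clinical recurrence between i2a and i2b. Where the SAP does want a higher threshold it says so, in the separately labelled sensitivity analysis of SAP 5.3.5.2. The Week 24 and Week 152 endpoint has no such label.

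At stake is whether exploratory recurrence at Weeks 24 and 152 means the same as recurrence in the primary analysis. In addition, two recurrence endpoints at Week 24, one strict and one without a threshold, could be programmed with different cut-offs for the same visit.

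**Working it through.** The plan gives no rate or power figure for this endpoint, so there is nothing to reproduce. The check is a classification.

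**Step 1: each score against each definition.** The modified score splits i2 into i2a and i2b.

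| Score | Primary, up to Week 48 (≥ i2a) | Week 24 cross over eligibility (i2a or greater) | Exploratory Week 24/152 (> i2a) |
|---|---|---|---|
| i0 | no | no | no |
| i1 | no | no | no |
| **i2a** | **yes** | **yes** | **no** |
| i2b | yes | yes | yes |
| i3 | yes | yes | yes |
| i4 | yes | yes | yes |

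Only i2a is classified differently.

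**Step 2: add the handling rules of SAP 5.5.2.** For exploratory binary endpoints, intercurrent events 1–4 give the unfavourable outcome, and so do data still missing afterwards. Event 4 is cross over to open-label guselkumab. For the Week 24 endpoint:

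- *Scoped, i2a, crosses over:* counted as recurrence through event 4. SAP 5.5.2 sets no visit cut-off, and the event window in SAP Table 7 runs from baseline to Week 48.
- *Scoped, i2a, no cross over and no other event in 1–4:* recurrence in the primary endpoint, not in the Week 24 endpoint.
- *Not scoped:* missing, so counted as recurrence.

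Two participants with the same i2a reading can therefore differ according to a discretionary cross over decision. A participant with no Week 24 examination counts as recurrence while one with an observed i2a does not.

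**Step 3: Week 152.** Confirmed recurrence at ≥ i2a on the Week 48 or a flare ileocolonoscopy already leads to cross over under Protocol 6.5.1. The sign therefore matters mainly for an i2a first seen at Week 152, which is not counted.

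**Step 4: can the effect be sized?** Ignoring events 1–4, let *s* be the fraction scoped at Week 24, *r* the rate of ≥ i2a among them, and *f* the i2a share of those scores. The reported rate is (1 − s) + s·r with ≥ i2a and (1 − s) + s·r·(1 − f) with > i2a, so the loss is s·r·f. The documents give none of these inputs for Week 24. Purely as an assumption, take s = 0.30, r = 0.50 and f = 0.20 to 0.40:

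- with ≥ i2a: 0.70 + 0.30 × 0.50 = 0.85
- with > i2a, f = 0.20: 0.70 + 0.30 × 0.40 = 0.82
- with > i2a, f = 0.40: 0.70 + 0.30 × 0.30 = 0.79

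The loss is 3 to 6 percentage points, and event 4 would reduce it further. This shows how the rules act; it is not an estimate.

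**The case against.** **The sign may be a printing matter.** SAP Section 3, Table 5 contains an underlined greater-than sign, and an underline can be lost when text is read from a PDF. This cannot be excluded, and the source file should be checked before editing. Against it, the strict sign stands in all four places across two documents, while SAP 1.1 shows ≥ for the primary endpoint in the same table.

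**Cross over is already handled.** A reader might infer that someone who crosses over at Week 24 for i2a would be reported as having no recurrence. That holds on the score alone, but SAP 5.5.2 as written counts cross over as unfavourable. The objection stands for participants who cross over and leaves those who do not.

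**Remission.** A reader might infer from "Endoscopic remission (modified Rutgeerts score <i2a) at 24 weeks after guselkumab SC induction" that i2a is neither recurrence nor remission at Weeks 24 and 152. The documents do not support this. That definition applies only to cross over participants after open-label induction. At the scheduled visits the endpoint is "Endoscopic remission (SES-CD of 3 or less) at Week 24, Week 48, Week 152", on a different scale, so a participant scored i2a can be in remission.

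**Size.** A reader might also infer that the recurrence rate falls by the i2a share, say from 50% to 30–40% with a share of 20–40%. The documents give no such share. The arithmetic would also need everyone to be examined and nobody counted through an intercurrent event, whereas the Week 24 examination is optional.

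**Importance.** The endpoint is exploratory: "the testing of these endpoints will not be controlled for multiplicity". SAP Section 1 says four participants were enrolled and the planned analyses no longer apply. This stands, and it limits the point to a correction of definition.

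**Conclusion.** The mismatch is real in the text as it stands and is confined to i2a. Followed as written, the exploratory endpoint does not count an i2a at Week 24 in a participant with no intercurrent event in categories 1–4, nor an i2a first seen at Week 152. The primary endpoint counts the same Week 24 reading.

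This rests on two assumptions: that the printed sign is what was intended, and that event 4 is applied over the Table 7 window. If events were cut off at the visit date, participants who cross over after the Week 24 reading would be missed as well. The frequency of i2a is not in the documents, so no effect on the rates is claimed. The primary analysis, the testing hierarchy and the sample size are untouched. Practical impact is low.

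**What to change.** Write ≥ i2a in place of > i2a for the Week 24 and Week 152 endpoint in Protocol 1.1 and 3 and in SAP 1.1 and 5.5.1. State the same threshold for the endpoint of recurrence up to Week 24 in SAP 5.5.1 and Protocol 9.4.4. If a stricter cut-off was meant, label it as such and give the reason. This concerns the analysis definition only; no change to the cross over rule is proposed.

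The cost is one symbol in four places and one clause in two, with no new data and no effect on the type I error control. The SAP still plans to report Rutgeerts scores for the four participants, so any recurrence label attached to those scores should use the single definition.
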